## Objectives

The primary objectives of this study are to investigate the effectiveness of IMM-101 combined with nivolumab in controlling advanced melanoma and to assess and describe the safety profile of the combination after a maximum of 18 months of treatment with IMM-101 + nivolumab. The safety and efficacy of the combination will be assessed in patients who are either previously untreated (cohort A), or whose disease has progressed during PD-1 blockade (cohort B) and compared with published data on the efficacy and adverse event profile of nivolumab alone.

The primary objectives are:

- To evaluate Overall Response Rate (ORR) after a maximum of 18 months treatment, in patients with advanced melanoma receiving IMM-101 + nivolumab. ORR in both previously untreated patients (cohort A) and in patients whose disease has progressed during PD-1 blockade (cohort B) will be evaluated using RECIST 1.1. ORR will also be assessed for subgroups based on PD-L1 status (positive or negative/undetermined) in cohort A patients.
- To evaluate the safety and tolerability of the combination of IMM-101 + nivolumab in patients with advanced melanoma by examining the profile of adverse events experienced.

The secondary objectives of the study are:

- To evaluate Progression-free Survival (PFS) after a maximum of 18 months treatment in patients with advanced melanoma receiving IMM-101 + nivolumab for both cohort A and cohort B, assessed by RECIST 1.1
- To evaluate Overall Survival (OS) and OS at 1 year in patients with advanced melanoma for both cohort A and cohort B.
- To evaluate changes in laboratory parameters
- To evaluate local tolerability (injection site reactions)

The exploratory objectives are:

- To evaluate the ORR in patients with advanced melanoma receiving IMM-101 + nivolumab using immune-related Response Criteria (irRC) for both cohort A and cohort B.
- To evaluate the Duration of Response and Time to Response in patients with advanced melanoma receiving IMM-101 + nivolumab for both cohort A and cohort B, assessed by RECIST 1.1.
- To evaluate Disease Control for patients in cohort B of the study only, defined as those patients with a response or stable disease (SD) based on RECIST 1.1. and assessed at each scan assessment point from Week 14 onwards.
- To evaluate Best Overall Response (BOR) for patients in cohort B to include any responses obtained following a change in therapy from IMM-101 + nivolumab to IMM-101 + ipilimumab, by including all tumour assessments on study.
- To evaluate the safety and tolerability of the combination of IMM-101 + ipilimumab in patients with advanced melanoma by examining the profile of adverse events experienced for any patients in cohort B of the study who took IMM-101 + ipilimumab as subsequent treatment.

	
 
Monitoring of selected markers of tumour burden and immunological status in patients receiving IMM-101 (to be reported separately to other endpoints).
 

Study Duration	The study will continue until all patients have had the opportunity of 18 months treatment on study.  The written consent document will include permission for the Investigator
	or designee to contact the patient's general practitioner (GP) for continued collection of survival data post study completion or in the event of withdrawal from the study. These data will be collected until database lock.
Principal Selection Criteria	A patient must meet all of the following inclusion criteria to be eligible to participate in this study:  1. Patient must have a histologically-confirmed diagnosis of advanced (unresectable Stage III) or metastatic (Stage IV) melanoma excluding uveal/ocular melanoma. Patients with unknown primary melanoma are eligible.  2. Patient has at least one measurable lesion by CT or MRI, according to RECIST 1.1.  3. Patient must have known BRAF V600 mutation status or consent to BRAF V600 mutation testing during the Screening Period.  4. Patients who have had prior radiotherapy must have completed this at least 2 weeks prior to study drug administration (Week 0, Visit 1). Prior adjuvant or neoadjuvant melanoma therapy is permitted if it was completed at least 6 weeks prior to enrolment (Week 0, Visit 1), and all related adverse events have resolved or stabilised.  5. Patient is considered suitable for treatment with nivolumab.  6. Patient provides signed informed consent for participation in the study.  7. Patient has an Eastern Cooperative Oncology Group (ECOG)/World Health Organisation (WHO) Performance Status of ≤1 at Day 0.  8. Patient has Screening laboratory values meeting the following criteria. These should be obtained within 14 days prior to first dose on study:  a. Haemoglobin (Hb) ≥9.0g/dL, absolute neutrophil count ≥1.5 x 10°/L, platelets ≥100 x 10°/L and White Blood Cells (WBC) ≥ 2.0 x 10°/L (blood transfusion to achieve these levels are not permitted within 2 weeks of this assessment).  b. Total bilirubin ≤1.5 x upper limit of normal (ULN), excluding cases where elevated bilirubin can be attributed to Gilbert's Syndrome.  c. Aspartate transaminase (AST; serum glutamic oxaloacetic transaminase [SGOT]), and alanine transaminase (ALT; serum glutamate pyruvate transaminase (FGOT), and creatinine ≤1.5 x ULN in presence of liver metastases.  d. Creatinine ≤1.5 x ULN
	e. Serum albumin ≥30g/L

Page 16 of 98

9. Patient is aged  $\geq$ 18 years.

For cohort A, the following inclusion criteria must also be met for a patient to be eligible to participate in this study:

- 1. Patient is treatment-naive (i.e. no prior systemic anticancer therapy for unresectable or metastatic melanoma).
- 2. Patient must have a tumour sample (archived tissue in the last 3 months or newly obtained biopsy) that is adequate for PD-L1 assessment prior to enrolment. Patients will be eligible to participate regardless of the level of PD-L1 expression. Patients with an inadequate archived sample may obtain a new biopsy and patients with an inadequate newly obtained biopsy may undergo one further re-biopsy at the discretion of the investigator.

For cohort B, the following inclusion criteria must also be met for a patient to be eligible to participate in this study:

- 1. Patient is either currently on (or has previously received) treatment with an anti-PD-1 therapy (monotherapy or in combination), for advanced melanoma and has progressive disease by RECIST 1.1 after at least 3 doses of anti-PD-1 given as monotherapy or at least 2 doses of anti-PD-1 given in combination regimes, and has not received any therapy since, for advanced melanoma. The last dose of PD-1 targeted therapy must have been received no more than 12 weeks prior to the start of Screening but more than 6 weeks prior to first IMM-101 administration. For all patients in cohort B, progression must have occurred during the PD-1 targeted treatment and the investigator has deemed it appropriate to continue/start treatment with nivolumab beyond disease progression.
- 2. Patients must have recovered from any AEs related to prior anti-PD-1 containing regime to Grade 1 or have resolved.
- 3. Patients with a BRAF mutation must have taken BRAF- and/or MEK-targeted therapy, unless patients are not candidates for, or have refused, these therapies. Anti-PD-1 therapy must be the current or last treatment for advanced melanoma prior to study entry.

A patient meeting any of the following exclusion criteria is not eligible to participate in this study:

- 1. Patient has uveal/ocular melanoma.
- 2. Patient has active brain metastases or leptomeningeal metastases. Patients with brain metastases are eligible for cohort B of the study only, if these have been treated and there is no MRI evidence of progression for at least 8 weeks after treatment is complete and within 21 days prior to first dose of study treatment administration.
- 3. Patient has previously received treatment with IMM-101.
- 4. Patient is either receiving concomitant treatment with another investigational product or has received such treatment within the 3 weeks prior to first IMM-101 administration.
- 5. Patient has any serious or uncontrolled medical disorder or co-existing active infection that, in the opinion of the Investigator, may increase the risk associated with study participation or study drug administration, impair the ability of the subject to receive protocol therapy, interfere with the patient's participation for the full duration of the study, or is not in the best interest of the patient to participate.
- 6. Patient has any previous or concurrent malignancy. Patients will not be excluded if they have had adequately treated carcinoma in situ of the cervix, basal cell carcinoma of the skin and/or non-melanoma skin cancer, or if previous malignancy was more than 5 years prior to Screening and there are no signs of recurrence.
- 7. Patient has previously experienced an allergic reaction to any mycobacterial product or any monoclonal antibody.
- 8. Patient has a history of non-infectious pneumonitis that required steroids or current pneumonitis.
- 9. Patient has documented history of clinically severe autoimmune disease or a syndrome that requires systemic steroids or immunosuppressive agents.
- 10. Patient has a known history of Human Immunodeficiency Virus (HIV) (HIV 1/2 antibodies).
- 11. Patient has a known history of or is positive for Hepatitis B (HBsAg reactive) or Hepatitis C (HCV RNA [qualitative] is detected).
- 12. Patient has received live vaccine within 30 days before Week 0, Visit 1
- 13. Patient is pregnant or breast-feeding. Female patients with reproductive potential must have a negative serum pregnancy test (β-human chorionic gonadotropin [β-hCG]) within 72 hours prior to first administration of study treatment. Both women and men must agree to use a medically acceptable, effective method of contraception throughout the treatment period and for at least 6 months after discontinuation of treatment.
- 14. Patient has used depot corticosteroids in the 6 weeks before initiation of Screening (signing of the informed consent form [ICF]).

Protocol No. IMM-101-015

Page 18 of 98 Final Version 2.0 incorporating Amendment 1, 16 December 2019

	
 
15. Patient has a condition requiring systemic treatment with either corticosteroids (> 10 mg daily prednisone equivalent) or immunosuppressant drugs (such as azathioprine, tacrolimus, cyclosporin) within the 14 days period before the first administration of IMM-101. Inhaled or topical steroids, and adrenal replacement steroid doses > 10 mg daily prednisone equivalent, are permitted in the absence of active autoimmune disease.
 
16. Patient has received a blood transfusion within 4 weeks prior to initiation of Screening.
 
17. In the opinion of the Investigator, the patient is unable or unwilling to comply with the protocol.
 
For cohort A, patients meeting any of the following criteria are also ineligible to participate in this study: 
 
Patient has received prior therapy with an anti-programmed cell death-1 (anti-PD-1), anti-PD ligand-1 (PD-L1), anti-PD-L2, anti-CD137 antibody, or anti-cytotoxic T-lymphocyte-associated antigen-4 (CTLA-4) agent.
 
 
 
For cohort B, patients meeting any of the following criteria are also ineligible to participate in this study: 
 
Patient has previously experienced an AE related to anti-PD-1 therapy which, in the investigator's opinion, makes them
 
 
 

Investigational Product	unsuitable for further treatment with nivolumab.  IMM-101 is a suspension of heat-killed whole cell M. obuense
Formulation Formulation	(NCTC 13365) in borate-buffered saline.
Dosage	A single 0.1 mL intradermal injection of IMM-101 (10 mg/mL).  Dosing of nivolumab to be in accordance with the prescribing information.  Dosing of ipilimumab, when used as subsequent treatment for patients in cohort B, to be in accordance with the prescribing information.
Administration	IMM-101 Dosing Regimen: The treatment regimen with IMM-101 will be one dose given every 2 weeks for the first 3 doses followed by a rest period of 4 weeks, then one dose every 2 weeks for the next 3 doses. This is followed by a dose every 4 weeks thereafter.
	During the study, at the discretion of the Investigator, the dose interval may be modified provided the minimum period between doses is at least 12 days (14±2 days) between visits 1-2, 2-3, 5-6 and 6-7. The 28 day interval ±2 days between other doses (3-5, 7-9 and all after this point) should be maintained, subject to skin reactions or other immune-related AEs as detailed below.
	IMM-101 is given via intradermal injection into the skin overlying the deltoid muscle, with the arm being alternated between each dose.
	Local skin reactions are expected but, in the event of an injection site reaction of ≥Grade 3 (severe) as measured by the NCI CTCAE v4.03, at the discretion of the Investigator, patients may be administered a half dose of IMM-101 (i.e., a single 0.05 mL intradermal injection of IMM-101) or the dosing interval may be increased or both. If the dosing interval is increased, the patient should attend the study site for safety assessments at least every 4 weeks.

	Nivolumab is to be administered in accordance with the prescribing information. When the patient starts on the study, the Investigator can choose to administer nivolumab using one of the following dosing regimens – 3mg/kg every 2 weeks, 240mg every 2 weeks or 480mg every 4 weeks. Ideally, the nivolumab dosing regimen chosen at the start of the study should be maintained (notwithstanding modifications due to AEs as described above). However, if a 480mg 4-weekly nivolumab dosing is not tolerated, the patient may be switched to a 240mg 2 weekly regimen. In instances when nivolumab and IMM-101 are given on the same day, IMM-101 will be administered first. If used on study for patients in cohort B, ipilimumab is to be administered every 3 weeks in accordance with the prescribing information. In instances when ipilimumab and IMM-101 are given on the same day, IMM-101 will be administered first. In the event of any immune-mediated adverse reactions of ≥ Grade 3 (severe), IMM-101 and nivolumab (or ipilimumab when used for cohort B) should be withdrawn, either until resolution of the event or permanently, at the discretion of the Investigator.
Prohibited Medication	Chronically administered systemic or depot corticosteroids or immunosuppressant drugs (such as azathioprine, tacrolimus, cyclosporin) should not be administered to patients in this study. No antineoplastic systemic chemotherapy or biological therapy are allowed and live vaccines and other investigational agents are also not permitted. Radiation therapy, apart from to a single solitary lesion after the first scheduled tumour assessment on study, should not be used.
Visit Schedule	The study will consist of two phases – Screening Phase and Treatment Phase. Details of the Study Schedule are shown in Appendix 1.
Safety and Tolerability Endpoints:	
 
The primary safety endpoint is:
 
Incidence, frequency and severity of AEs, SAEs, treatment related AEs, immune-related AEs, Grade 3 and above AEs and AEs leading to IMM-101 discontinuation or study withdrawal experienced during treatment with IMM-101 + nivolumab for both cohorts
 
Secondary safety endpoints are:
 
Incidence and frequency of laboratory parameter abnormalities
 
Change from baseline values in laboratory parameter values
 
Incidence and frequency of local injection site reactions.
 
An exploratory safety endpoint is:
 
For any patients in cohort B of the study who took IMM-101 + ipilimumab as subsequent treatment, the incidence, frequency and severity of AEs, SAEs, treatment related AEs, and immune-related AEs from the start of treatment with ipilimumab.
 

Efficacy Endpoints:	
 
The primary efficacy endpoint is:
 
Overall Response Rate (ORR) calculated from the BOR of patients as assessed by RECIST 1.1. ORR will be assessed at the end of study or when all patients have withdrawn, if this is sooner. For cohort B,
 

	ORR will apply to BOR from tumour assessments during IMM-101 + nivolumab treatment only. ORR and BOR will also be assessed for

Page 20 of 98

subgroups based on PD-L1 status (positive or negative/undetermined) in cohort A patients.

The secondary efficacy endpoints of this study are:

- Progression-free survival (PFS) assessed by RECIST 1.1 after a maximum of 18 months treatment in patients receiving IMM-101 + nivolumab.
- Overall survival (OS) and OS at 1 year, for both cohort A and cohort B. The median OS (if applicable) and OS rate at 12 months will be estimated.

Exploratory efficacy endpoints are:

- ORR using irRC in patients in both cohort A and cohort B receiving IMM-101 + nivolumab.
- Duration of Response and Time to Response for both cohort A and cohort B receiving IMM-101 + nivolumab and assessed by RECIST 1 1
- Disease Control, for patients in cohort B of the study only and defined as those patients with a response or stable disease based on RECIST 1.1., assessed at each scan assessment point from Week 14 onwards.
- BOR for cohort B to include any responses obtained following a change in therapy from IMM-101 + nivolumab to IMM-101 + ipilimumab.
- Immunological markers from blood and biopsy samples (to be reported separately to other endpoints).

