## 3.3.3 Study Number IMM-101-002 and IMM-101-002A

In May 2011, IMM-101-002, (IMAGE1, Immune Modulation And Gemcitabine Evaluation 1) a randomised, open-label, proof of concept, Phase 2 study comparing GEM, with and without IMM-101, as first-line treatment for advanced pancreatic cancer was initiated. The study recruited patients at 20 sites in the United Kingdom (UK), Spain, Italy, Ireland and Cyprus over a 2-year period ending in August 2013. A total of 110 patients were randomised: 75 to the IMM-101 plus GEM group, 35 to the Control (GEM alone) group. This study has now reported. The safety and efficacy data are presented in the IMM-101 IB.

The median overall survival (OS) was 6.7 months for the IMM-101 treated group and 5.6 months for the Control group (hazard ratio [HR] 0.68; 95% confidence interval [CI] 0.44, 1.04; p = 0.076). For the subgroup of patients with metastatic disease (84% of population), the median OS was 7.0 months for the IMM-101 treated group and 4.4 months for the Control group (HR 0.54; 95% CI 0.33, 0.87; p = 0.011). Median progression-free survival (PFS) was also improved for the IMM-101 treated group at 4.1 months for the IMM-101 treated group and 2.4 months for the Control group (HR 0.58; 95% CI 0.37, 0.91; p = 0.018). For the subgroup of patients with metastatic disease, the median PFS was 4.4 months for the IMM-101 treated group and 2.3 months for the Control group (HR 0.46; 95% CI 0.28, 0.75; p = 0.002). Baseline factors analysed were not found to have any statistically significant impact on the efficacy results.

The frequency of AEs was similar in the IMM-101 treated group compared to the Control group (3.05 AEs per month on study for the IMM-101 treated group and 3.59 AEs for the Control). The most common adverse events of Grade 3 or higher were asthenia (10.8% in the IMM-101 treated group and 2.9% in the Control group, fatigue (5.4% v. 11.4%), white blood cell count decreased (2.7% v. 11.4%) and neutropenia (14.9% v. 11.4%).

Injection site reactions, viewed as a normal and predicted reaction to exposure to a preparation of mycobacterial antigens, were consistent for this class of product and were well tolerated by the patients.

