### 11.1.3 Safety and Tolerability Endpoints

The primary safety endpoints include the following:

• Incidence, frequency and severity of AEs, Serious AEs, treatment-related AEs (related to IMM-101 and/or nivolumab/ipilimumab (as applicable), immune-related AEs (as listed in the SmPC for nivolumab), Grade 3 and above AEs and AEs leading to IMM-101 discontinuation or study withdrawal throughout the study.

The secondary safety endpoints include the following:

- Incidence and frequency of laboratory parameter abnormalities
- Change from baseline values in laboratory parameter values
- Incidence and frequency of local injection site reactions.

Page 77 of 98

Exploratory safety endpoints include the following:

• For the subgroup of patients in cohort B who receive IMM-101 + ipilimumab as subsequent treatment: The incidence, frequency and severity of adverse events, serious adverse events, treatment-related adverse events and immune-related adverse events (as listed in the SmPC for ipilimumab) experienced following the start of ipilimumab treatment up to the end of the study.

Treatment-emergent AEs (TEAEs) are defined as AEs occurring after the first dose of IMM-101. Only TEAEs will be presented in summary tables and all AEs (i.e., TEAEs and non-TEAEs) will be listed by patient within cohort.

TEAEs will be summarised by MedDRA system organ class and preferred term using standard incidence and frequency tables. The incidence of TEAEs will be presented as the proportion of patients with at least one AE by system organ class and preferred term and frequency of TEAEs will be calculated as the number of events by system organ class and preferred term.

Treatment-related AEs are defined as AEs which are related to study treatment (IMM-101 and/or nivolumab, and/or ipilimumab if after ipilimumab dosing in cohort B). Related AEs will be those assigned by the investigator as definitely, probably or possibly related to study treatment or with an unknown relationship. Relatedness will be assessed to each of IMM-101, nivolumab and ipilimumab separately as well as for the combined treatment combination. The incidence and frequency of treatment-related AEs, SAEs, and immune-related AEs will be presented, as for all TEAEs.

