For cohort B patients, only TEAEs occurring prior to the start of treatment with IMM-101 + ipilimumab or TEAEs assessed as related (i.e. definitely, probably or possibly related) to nivolumab will be included in the primary safety endpoint evaluations. For the exploratory evaluation of safety, only TEAEs occurring after the start of treatment with IMM-101 + ipilimumab will be included (including any TEAEs related to nivolumab but occurring after the start of ipilimumab).

Grade 3 and above AEs, AEs leading to study withdrawal and AEs leading to death will be summarised by cohort, if present, and listed as above.

The incidence, frequency and severity and type of all TEAEs (following the start of IMM-101 administration, regardless of combination therapy received) will be included in the data presentations, for the combined cohorts.

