5.12 Exposure and Compliance

An exposure summary will include the time on study, the overall exposure of each of IMM-101, nivolumab and ipilimumab and the total dose exposure of nivolumab. The number of doses of IMM-101, and whether they were full or half doses will also be summarised.

The time on study will be calculated in months as (date of completion/withdrawal - date of first IMM-101 administration + 1)/30.4375.

Overall exposure to each of IMM-101, nivolumab and ipilimumab will be calculated in months as (date of last administration – date of first administration + 1)/30.4375.

Total nivolumab exposure will be calculated in mg across the duration of the subject's participation as the sum of the total dose administered at each nivolumab dosing visit for each subject.

Compliance will be summarised for IMM-101, nivolumab and ipilimumab separately for each visit.

For IMM-101, the number of subjects receiving treatment and whether these were full or half doses, the number of subjects not dosed, the reason for not dosing, the number of subjects with delayed dosing and the reasons for the delay will be summarised.

For nivolumab, the number of subjects receiving the infusion and the reasons if they did not receive the infusion, the number of subjects with delayed infusion and reasons for delayed infusion, the dosing regimen chosen and whether the regimen was modified will be summarised. The number of subjects who received less than, more than or exactly the planned dose will also be summarised.

For ipilimumab, the number of subjects receiving the infusion and the reasons why they received the infusion will be summarised. For each of the four infusions, the

number of subjects with delayed infusion and reasons for delayed infusion and the number of subjects who received less than, more than or exactly the planned dose will also be summarised.

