5.15 SAFETY EVALUATION

5.15.1 Adverse Events

AEs will be coded using the latest MedDRA dictionary version. The version used will be indicated in the data summaries and listings.

A treatment-emergent adverse event (TEAE) is defined as an AE that started on or after the start of the administration of IMM-101. If adverse event dates are incomplete and it is not clear whether the adverse event was treatment-emergent, it will be assumed to be treatment-emergent.

The relationship with each study treatment will be entered in to the eCRF for IMM-101, nivolumab and ipilimumab. A treatment-related TEAE is defined as a TEAE that is possibly, probably or definitely related to the study treatment. For each treatment, where the TEAE has a missing relationship it is assumed to be related to the treatment for analysis purposes.

A summary table will present the following:

- TEAEs (events and subjects).
- Serious TEAEs (events and subjects).
- Treatment-related TEAEs (relating to IMM-101 and/or nivolumab and/or ipilimumab) (events and subjects).
- Immune-related TEAEs (events and subjects).
- TEAEs with a Common Terminology Criteria for Adverse Events (CTCAE) Grade of 3 or above (events and subjects).
- TEAEs leading to discontinuation of IMM-101 (subjects only).

- TEAEs leading to withdrawal from study (subjects only).
- TEAEs leading to death (subjects only).
- TEAEs by CTCAE grade (1 to 5) (subjects only).
- TEAEs by severity (mild/moderate/severe/life threatening/death) (subjects only).
- TEAEs by relationship to study treatment and the pooled study treatment related category (subjects only).

In the above summaries, if a subject experienced more than one TEAE, the subject will be counted once using the most related event for the “by relationship to study treatment” and “related to IMM-101/nivolumab/ipilimumab” summaries, at the worst grade for the “by CTCAE grade” summary, and at the worst severity for the “by severity” summary.

A summary table will also be produced for Cohort B subjects only for AEs which occur at or after the start of infusion of ipilimumab. Any nivolumab related TEAEs occurring after the start of ipilimumab administration will be included. The summary will present the following:

- TEAEs (events and subjects).
- Serious TEAEs (events and subjects).
- Treatment-related TEAEs (relating to IMM-101 and/or ipilimumab) (events and subjects).
- Immune-related TEAEs (events and subjects).

The following tables will be presented:

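### Adverse event frequency in the primary safety endpoint is a bare event count, so it is confounded by exposure; a matched rate per patient-month should stand beside it

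*Protocol*

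**What the plan says.** For the primary safety endpoint, the protocol synopsis (Section 2, Safety and Tolerability Endpoints) lists "Incidence, frequency and severity of AEs, SAEs, treatment related AEs, immune-related AEs, Grade 3 and above AEs and AEs leading to IMM-101 discontinuation". It thus names three measures: incidence, frequency and severity. Protocol 11.1.3 defines the first two:

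- Incidence: "The incidence of TEAEs will be presented as the proportion of patients with at least one AE by system organ class and preferred term".
- Frequency: "frequency of TEAEs will be calculated as the number of events by system organ class and preferred term".

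In SAP 5.15.1 the summary table opens with the line "TEAEs (events and subjects", and the serious, treatment-related, immune-related and Grade 3 or above lines are built the same way. Neither document divides events by time.

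The objectives (Protocol Sections 2 and 4; SAP 2.1) say the safety and efficacy of the combination will be "compared with published data on the efficacy and adverse event profile of nivolumab alone". SAP 5.4 shows adverse events by cohort and overall. Protocol 11.1.3 adds that all TEAEs, whichever partner drug was being given, "will be included in the data presentations, for the combined cohorts".

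Time at risk is set in several places. One dose of IMM-101 is enough to enter the safety set (Protocol 11.7.1; SAP 5.3). Dosing may last up to 18 months in either cohort (Protocol 7.4). AEs are followed for up to 30 days after the last study treatment, but related SAEs are recorded whatever the interval (Protocol 9.5). For Cohort B, the primary safety evaluation takes TEAEs before ipilimumab starts, plus TEAEs judged related to nivolumab (Protocol 11.1.3).

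For the sponsor's earlier randomised pancreatic study, Protocol 3.3.3 reports AE frequency over time: "3.05 AEs per month on study for the IMM-101 treated group and 3.59 AEs for the Control".

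**The concern.** An event count is the product of the number of patients, the event rate and the time observed. When time at risk varies widely and is not in the denominator, a higher count may mean more toxicity or simply longer treatment. Treatment normally ends at progression, so a patient who stays on treatment longer has more time to accrue events.

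This matters in two places. The external comparison with nivolumab alone is a written objective, and a count from 18 or 8 patients with their own follow-up cannot be set against another trial's figures. The AE tables also place Cohort A, Cohort B and an overall column together, which invites reading across columns whose time at risk may differ.

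**Working it through.** The plan gives no AE rate, exposure assumption or sample size calculation to reproduce, so the checks below are direct arithmetic.

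**1. Range of time at risk.** Window in months = (days from first to last dose + 30) / 30.4375. The 30 days come from Protocol 9.5 and the divisor from SAP 5.12.

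- One dose: 30 / 30.4375 = 0.99 months.
- Last dose at Week 76, the final IMM-101 visit in Appendix 1: (76 × 7 + 30) / 30.4375 = 562 / 30.4375 = 18.5 months.
- Ratio: 562 / 30 = 18.7. If nivolumab is given at Week 78, the window is 576 / 30.4375 = 18.9 months and the ratio 19.2.

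**2. Effect on counts when toxicity is equal.** Assume a true rate of 1 event per patient-month in both cohorts and the planned sizes, 18 and 8. Events = patients × rate × mean months. The mean exposures are assumptions, because the documents give none.

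| Mean months A, B | Events A | Events B | Events per patient, A:B | Rate A, B |
|---|---|---|---|---|
| 6, 6 | 108 | 48 | 1.0 | 1.0, 1.0 |
| 9, 6 | 162 | 48 | 1.5 | 1.0, 1.0 |
| 9, 4 | 162 | 32 | 2.25 | 1.0, 1.0 |
| 12, 4 | 216 | 32 | 3.0 | 1.0, 1.0 |
| 12, 3 | 216 | 24 | 4.0 | 1.0, 1.0 |

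Any other common rate leaves the per-patient ratio unchanged. At 3.05 per month, 12 and 3 months give 36.6 and 9.15 events per patient, again four-fold.

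**3. The sponsor's earlier study as an example.** The reported rates give 3.05 / 3.59 = 0.85. Mean time on study is not given, so two medians from Protocol 3.3.3 serve as assumed proxies.

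- Median PFS (4.1 and 2.4 months): 3.05 × 4.1 = 12.5 and 3.59 × 2.4 = 8.6 events per patient, ratio 1.45. The direction reverses.
- Median OS (6.7 and 5.6 months): 3.05 × 6.7 = 20.4 and 3.59 × 5.6 = 20.1, ratio 1.02. The difference disappears.

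**4. Whether SAP 5.12 already supplies the denominator.** "The time on study will be calculated in months as" completion or withdrawal minus first IMM-101 dose, plus one day, over 30.4375. That interval includes any ipilimumab period, and also off-treatment scan follow-up for patients who stop for reasons other than progression (Protocol 5.1). Exposure to each drug runs from first to last dose: 1 / 30.4375 = 0.03 months for one dose, against a 0.99-month AE window, and 533 / 30.4375 = 17.5 months to Week 76, against 18.5. In Cohort B, IMM-101 exposure continues through ipilimumab. None of these is the AE risk window.

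**5. Whether incidence escapes the problem.** With a constant hazard, incidence = 1 − exp(−hazard × months). At an assumed 0.05 per month this is 18% at 4 months, 45% at 12 and 59% at 18. Incidence also depends on time, but it is a bounded per-patient percentage.

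**The case against.** The strongest reply is that frequency is one of three measures. Incidence and severity are reported beside it, and SAP 5.15.1 counts subjects in every category. Apart from the one per-month sentence, the protocol mostly quotes earlier AE data as percentages, and nothing says that event counts are what will be set against nivolumab. The documents do not show that nivolumab AEs per patient-month have been published. The study is descriptive and non-comparative (Protocol 11.3; SAP 2.3), and exposure is tabulated, so a crude rate could be worked out. All of this stands, and it limits the point to a missing presentation. It does not make the count interpretable as a measure of frequency.

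A reader might infer more than the documents support:

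- *That the counts merely measure exposure.* They mix patients, rate and time; they are confounded by exposure.
- *That Cohort B will look safer because it is treated for less time.* Both cohorts share the 18-month maximum and may be treated beyond progression (Protocol 7.5). Shorter exposure in Cohort B is plausible but assumed, and the plan draws no conclusion between cohorts.
- *That Cohort B's primary safety period simply ends at ipilimumab.* Protocol 11.1.3 also admits nivolumab-related TEAEs, without limiting them to before the switch.
- *That a rate removes the problem.* It compares cleanly only if the hazard is roughly constant. IMM-101 is given more often in the first 12 weeks than later (Protocol 5.1), and Protocol 3.5 says injection site reactions increase over time.

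**Conclusion.** The point holds as a gap in presentation. Frequency, as defined, is an event count with no person-time, while possible time at risk spans about 1 to 18.5 months per patient. The count alone cannot support the stated comparison with published nivolumab data, and it should not be read across the cohort and overall columns. Incidence and severity remain, so the primary safety endpoint is not invalid.

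The 19-fold range follows from the documents' own rules and describes what is possible for individual patients; it is not a forecast of the difference between cohorts. The 1- to 4-fold figures rest on assumed mean exposures. The rate of 3.05 per month comes from pancreatic cancer treated with gemcitabine and serves only as an illustration. The reversal in the earlier study depends on using median PFS as a proxy for time on study; with median OS the counts are about equal.

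**What to change.** In SAP 5.15.1, add events per patient-month by cohort, beside the counts and incidence, for all, serious, treatment-related, immune-related and Grade 3 or above TEAEs on IMM-101 + nivolumab.

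- **Window.** Use the same one for events and person-time: from first IMM-101 dose to the earliest of 30 days after last study treatment, first ipilimumab dose (Cohort B), death, or end of study or data cut-off.
- **Events outside it.** Show nivolumab-related TEAEs after ipilimumab starts, and late related SAEs, as counts only. Otherwise they would enter the numerator with no matching time at risk.
- **Use.** Base any statement about frequency across cohorts or against other data on this rate. Where no comparable rate exists, use incidence and report it with the exposure summary.

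The cost is one new person-time derivation, applied to five TEAE categories by cohort, because time on study in SAP 5.12 is not the right denominator. Dosing dates, including those for ipilimumab, are already collected (SAP 5.11). The design and data collection do not change. Since the average rate assumes a roughly constant hazard, say so in a table footnote and keep incidence alongside it.
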